STOP Leg Clots

-

Swedish-international multicenter Trial of Outpatient Prevention of Leg Clots

**Prevention of thromboembolism and failed healing during lower
limb immobilization –
a multicenter study with adjuvant intermittent pneumatic
compression therapy**

Date of document: 200901

Identifiers: NCT03259204 Unique Protocol ID: 2017-00202

STOP Leg Clots -

Swedish-international multicenter Trial of Outpatient Prevention of Leg Clots

Prevention of thromboembolism and failed healing during lower limb immobilization –
a multicenter study with adjuvant intermittent pneumatic compression therapy

Purpose and Aims

Complications related to lower limb immobilization, such as venous thromboembolism (VTE) and delayed healing, after musculoskeletal trauma and reconstructive surgery represent increasing problems. The National Health Service in England has identified prophylaxis of VTE as the number one prioritized intervention^{1 2}.

As a result of trauma and post-operative lower limb immobilization and associated impaired neuro-vascular supply, patients exhibit an increased risk of VTE and hampered healing. Pharmacoprophylaxis for VTE in patients with lower-leg immobilization has, however, demonstrated low or non-effectiveness^{3 4 5}. Thus, there is no consensus for prevention, and a need for novel treatment strategies^{1 2 4}.

Our hypothesis is that leg immobilization calls for promoted blood circulation using adjuvant mechanical compression. This intervention, in the form of intermittent pneumatic compression (IPC) therapy, targets the primary cause of impaired neuro-vascular flow. IPC might reduce the risk of VTE and improve healing by respectively increasing the local supply of anticoagulants and healing mediators.

We aim to demonstrate that adjuvant, outpatient IPC-therapy in lower-leg immobilized patients, compared to treatment-as-usual, reduces VTE-incidence and improves healing. This VTE-preventive intervention can without delay be adapted in daily health care in order to increase patient safety and reduce costs as compared to pharmacological alternatives.

The primary outcome measure is the VTE-incidence at the end of immobilization, i.e. about at six weeks. Secondary outcome measures are patient-reported outcome assessed with validated scores, and effects on healing callus production with microdialysis and levels of profibrinolysis factors.

Survey of the Field

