Thus, it remains to show if prolonged adjuvant IPC therapy during the whole 6 weeks immobilization period could reduce the incidence of VTE in leg-immobilized patients, also in patients with fractures. Can the IPC treatment synchronously enhance the healing process so that it will lead to a long-term increased patient-reported outcome? Recent studies suggest that the increased neuro-vascular flow induced by IPC enhances the healing process¹⁵.

Research question

The primary research question is:

- Does addition of IPC to patients with lower limb immobilization in routine care, reduce the incidence of VTE up to the end of immobilization, i.e. 6-8 weeks.

Secondary questions are:

- Can adjuvant IPC during leg immobilization enhance fracture/soft tissue healing and improve patient-reported outcome?
- Does IPC reduce VTE incidence by upregulation of profibrinolysis?

Variables and measures

Primary outcome (binary), VTE, is defined as symptomatic or asymptomatic deep venous thrombosis (DVT) assessed at six weeks of immobilization by screening compression duplex ultrasound (CDU), or symptomatic pulmonary embolism detected by computer tomography. Assessors of CDU will be skilled ultrasonographers, masked to the treatment allocation⁹. The CDU-examination will document absence/presence of thrombus in the calf, popliteal and femoral veins separately, as previously described⁹. All positive examinations and those considered technically difficult will be reviewed by a specially trained vascular physician (blinded to the treatment allocation), who will establish the diagnosis and classify the examination result as absence or presence of thrombus. This will show the incidence of VTE in each group.

We acknowledge that the CDU assessment of DVT will be the dependent measure of outcome since DVT is more common than pulmonary embolism. CDU screening (surrogate outcome), can be justified because of the clinical significance attributed to even asymptomatic DVTs, which today are known to cause a high rate of pulmonary embolism, affect the patient outcome¹⁶ and are treated by most clinicians with anticoagulant therapy¹⁰. To reliably confirm or refute an effect of IPC on survival or clinical pulmonary embolism a

randomized trial would require a sample size of several tens of thousands of patients; this is not currently possible.

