Intervention: There is a need for new VTE prophylactic methods, especially in lower limb immobilized patients. IPC has been demonstrated cost effective both as adjuvant and versus no pharmacoprophylaxis in hospitalized patients by NICE. However, in an outpatient setting there are yet only recent short-term data of the efficacy of IPC. There is a need for data on the efficacy of IPC during long-term leg immobilization to inform guidelines.

The intervention, *addition of IPC to routine care*, will be administered in the emergency department or in the outpatient clinic. Patients will during the six weeks of lower limb immobilization receive bilateral calf IPC (Venaflo Elite, DJO LLC, Vista, CA, USA) applied under an orthosis (Aircast® AirSelect Elite, DJO LLC, Vista, CA, USA). This IPC-system delivers rapid inflation and graduated sequential compression. The IPC device is mobile and should therefore not restrict patient mobilization, but can be taken off if the patient wants to mobilize independently. The patients will be instructed to apply the IPC-therapy continuously, both day and night. Compliance with the treatment will be registered by both the patient and by the device⁹. American College of Chest Physicians recommend that efforts should be made to achieve 18 h of daily compliance with IPC in hospitalized patients¹⁷. However, there are no recommendations for mobile outpatients. Outpatients were in our recent study recommended at least 6h daily therapy, and in this study we will increase the recommendation to 10h/daily. Graduated compression stockings are part of IPC-care and these should be applied and worn under the IPC sleeves on both legs. IPC will be discontinued if the patient declines to continue IPC or had adverse effects of the IPC that warrants removal. At the 2 and 6 weeks visit the orthosis will be removed by a nurse and the patient will be examined by an orthopaedic surgeon (masked to the treatment allocation), who will document compliance and adverse events. At the 6 weeks visit the patient will also be sent for CDU-examination, which will document the main outcome. Patients will during the six weeks leg immobilization be weight-bearing with crutches or non-weight-bearing with crutches according to the preference of the orthopedic surgeon (masked to the treatment allocation). Weight-bearing will be recorded and accounted for in the statistical analysis.

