Comparator: Since there are no documented highly effective therapies for DVT reduction during leg immobilization, and guidelines vary regarding prophylaxis, we chose to use treatment-as-usual as a comparator, regardless of LMHW use or not^{3 4}. Based on our calculations less 10% of the patients will receive LMHW in clinical practice and our power calculations has taken this into account. NICE has stated that LMWH is not a feasible general treatment, especially health economically, during six weeks for all patients with leg immobilization. One review, including 1,490 patients from six randomized trials, showed a small reduction in DVTs using LMHW⁸. However, they concluded that more research is needed to develop more effective and safe thromboprophylactic treatments. Moreover, since a study with LMHW as a comparator would necessitate too many patients - this was not an option. The main research question remains: Is adjuvant IPC more effective than routine care for reducing the incidence of VTE in patients during lower limb immobilization? The usage of no general VTE-prevention in the comparator group is moreover justified since a DVT-screening will be performed on all patients. LMWH vs. no LMWH will be accounted for in the statistical analysis. If a VTE is detected we will follow clinical guidelines and initiate

pharmacological VTE-treatment.

The comparator, **routine care**, lower limb immobilization will be administered by normal routine in the emergency department or in the outpatient clinic. Routine care include that the lower limb will be immobilized in an orthosis or a below-knee plaster cast according to local routines. At the 2 and 6 weeks visit the orthosis/plaster cast will be removed by a nurse who will document compliance. Subsequently, the patient will be examined by an orthopaedic surgeon (masked to the treatment allocation), who will document adverse events. At the 6-8 weeks visit the patient will also be sent for CDU-examination, which will document the main outcome. Patients will during the six weeks leg immobilization be weight-bearing with crutches or non-weight-bearing with crutches according to the preference of the orthopedic surgeon (blinded to the treatment group). Weight-bearing will be recorded and accounted for in the statistical analysis.

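### The primary-outcome ultrasound is scheduled at 6 weeks in the IPC arm and at 6-8 weeks in the control arm, and no passage sets one window for both

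*Combined protocol and SAP*

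**What the plan says.** The two arm descriptions in Study Design (PICO) use the same sentence with different times.

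- **Intervention (IPC):** "At the 6 weeks visit the patient will also be sent for CDU-examination, which will document the main outcome".
- **Comparator (routine care):** "At the 6-8 weeks visit the patient will also be sent for CDU-examination, which will document the main outcome".

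The Comparator paragraph also uses six weeks elsewhere: "At the 2 and 6 weeks visit the orthosis/plaster cast will be removed by a nurse who will document compliance", and "Patients will during the six weeks leg immobilization be weight-bearing with crutches".

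The statements that apply to both arms differ among themselves.

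- **Purpose and Aims:** "The primary outcome measure is the VTE-incidence at the end of immobilization, i.e. about at six weeks".
- **Research question:** whether IPC will "reduce the incidence of VTE up to the end of immobilization, i.e. 6-8 weeks".
- **Variables and measures:** "asymptomatic deep venous thrombosis (DVT) assessed at six weeks of immobilization by screening compression duplex ultrasound (CDU".
- **Study Design, Outcome paragraph:** VTE at six weeks post-immobilization. Taken literally this is six weeks after immobilization ends, but it may be loose wording for six weeks after it began.

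The Statistical analysis plan gives no scan window. Its model for binary outcomes adjusts for the minimization factors and weight-bearing. Surgery and LMWH use are to be accounted for according to the design section. Scan time is not mentioned in either place.

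**The concern.** Variables and measures accepts that DVT found by ultrasound will drive the primary outcome. An asymptomatic DVT found at a single screening scan has no onset date, so the scan date sets the length of observation. If one arm is scanned later on average, the comparison mixes the treatment effect with a difference in observation time.

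Masking the ultrasonographer protects how the scan is read, not when it is booked. Intention-to-treat analysis keeps patients in their randomized groups but does not equalize follow-up. The planned covariates would not remove the difference either.

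The direction cannot be known in advance. Later scans could find more thrombi, which would favour IPC. They could find fewer, if some thrombi are no longer detectable, which would count against IPC. At least 20 hospitals have to apply this text, and they could reasonably read it in different ways.

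**Working it through.** **1. Does any reading reconcile the text?** The natural candidate is that 6-8 weeks is a common window for both arms.

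- For: the Research question gives 6-8 weeks for the trial as a whole.
- Against: it gives that range as the end of immobilization. Elsewhere immobilization lasts six weeks, as in Survey of the Field ("prolonged adjuvant IPC therapy during the whole 6 weeks immobilization period") and in both arm descriptions.
- Against: the Intervention sentence gives 6 weeks with no range.

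The text therefore does not decide between a common window and an arm difference.

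**2. The plan's own power.** Inputs from Estimated sample size and power: 28% vs 20%, alpha 0.05 (taken as two-sided), 1400 patients less 10%. At 1:1 allocation, n = 1400 × 0.9 / 2 = 630 per arm.

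Power = Φ[(Δ − 1.96·s0)/s1], with s0 = √(2p̄(1−p̄)/n) and s1 = √((p1(1−p1) + p2(1−p2))/n).

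Here s0 = 0.02406 and s1 = 0.02396, so Φ[(0.08 − 0.04716)/0.02396] = Φ(1.371) = 91.5%. The stated 90% reproduces. A common scan window changes none of these inputs.

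**3. Illustration: later control scans find more DVT.** The documents give no DVT rate after week 6. The only time course is for controls in the earlier ATR trial (Survey of the Field): 37% at week 2 and 50% at week 6. Two extrapolations past week 6:

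- Constant hazard: ln(0.63/0.50)/4 = 0.0578 per week. Extra risk after w weeks = 0.50 × (1 − e^(−0.0578w)).
- Linear: (50 − 37)/4 = 3.25 points per week.

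Both are scaled by 28/50 = 0.56 to the planned control rate. With no true effect and 28% in the IPC arm, the chance of a significant result favouring IPC follows from the formula in step 2.

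| Mean control delay | Extra control risk, hazard / linear (points) | Chance of significance favouring IPC, hazard / linear |
|---|---|---|
| None, or no new detectable DVT after week 6 | 0 | 2.5% |
| Half a week | 0.80 / 0.91 | 5.0% / 5.5% |
| One week | 1.57 / 1.82 | 8.9% / 10.6% |

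Example (one week, linear): 3.25 × 0.56 = 1.82 points; Φ[(0.0182 − 1.96 × 0.02554)/0.02554] = Φ(−1.25) = 10.6%. A one-week mean delay corresponds to all IPC scans at week 6 and control scans spread evenly over weeks 6-8.

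**4. Sensitivity to the assumed hazard.** Suppose instead a constant hazard from time zero that reaches 28% at week 6, so that risk at week w = 1 − 0.72^(w/6). Control scans at 6.5, 7 and 8 weeks then show 29.9%, 31.8% and 35.5%. The spurious differences are 1.9, 3.8 and 7.5 points, and the chances of significance favouring IPC are about 12%, 32% and 81%. The week 8 figure is the extreme in which every control is scanned at the end of the window.

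**5. Illustration: the opposite direction.** Suppose 5% of control thrombi are no longer detectable and none are new. The control rate is 0.28 × 0.95 = 26.6%, a shift of −1.4 points. Power against 20% is Φ[(0.066 − 1.96 × 0.02382)/0.02375] = 79.2%, down from 91.5%. The 5% is an assumption chosen for illustration.

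For scale, the plan gives 4 points as its minimum clinically relevant absolute reduction.

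**The case against.** The strongest reply is that this is a slip in one phrase. The section that defines the endpoint gives six weeks for both arms, and the Intervention paragraph agrees. The Comparator paragraph itself speaks of 2- and 6-week visits and six weeks of immobilization, and it describes no separate later visit for controls. Six weeks with a tolerance to eight would fit several of the statements, and nothing expresses an intention to scan controls later. This stands as a plausible account of how the text arose. It does not remove the need to correct it, because a site reading the arm descriptions finds two different instructions and no passage ranks one above the other.

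The second reply is that the figures depend on assumptions. This also stands. Steps 3 and 4 differ by a factor of about two for the same delay. The ATR figures come from weeks 2-6, before the week-6 cast removal, and are treated as cumulative incidence in the same patients, which the protocol does not state. No time course is given for ankle fracture, which supplies at least 1000 of the 1400 patients. IPC scans may slip as well, which would narrow any gap. The figures show what could be at stake and are not the reason for the finding.

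Third, the time origin is secondary. The primary outcome is counted in weeks of immobilization, whereas falls, a different variable, are counted from enrollment. An unclear origin affects both arms alike and is not a source of arm bias. It matters only because a window needs a stated starting point.

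Finally, an analysis adjusted for scan time conditions on a post-randomization variable, and the documents do not say that the scan date is captured. Both limits are carried into the fix.

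**Conclusion.** The concern holds and should be fixed. The arm texts give different times for the scan that largely determines the primary outcome, and the rest of the document does not resolve the difference. Confidence is high for the inconsistency itself. Whether the arms would actually be scanned at different times, by how much, and with what direction of bias cannot be determined from the documents.

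Under the ATR-based extrapolation, a mean control delay of half a week to one week gives 0.8 to 1.8 points of spurious benefit and a 5% to 11% chance of a false finding for IPC, against a nominal 2.5%. If no new detectable DVT arises after week 6, there is no bias from new events. A steeper assumed hazard gives more, and loss of detectable thrombi reverses the sign. The sample size and stated power are unaffected by the correction.

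**What to change.** 1. Reconcile Purpose and Aims, Research question, Variables and measures, and the Intervention, Comparator and Outcome paragraphs to one scan time and one visit window. These should be identical in both arms and counted from one stated origin, such as randomization or the start of immobilization. The time, window and origin are for the sponsor to choose.
2. Confirm that the scan date is recorded for every patient, and report time from the chosen origin to scan by arm.
3. If scan times differ between arms, add a supportive sensitivity analysis beside the intention-to-treat analysis, for example with scan time as a covariate or restricted to a narrow interval in which both arms were scanned. State that it conditions on a post-randomization variable and is uninformative if the arms' scan times hardly overlap. For that reason the wording correction comes first.

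The cost is protocol wording, one timing table and at most one supportive analysis. Some control scans may need rebooking; how many depends on actual timing, which the documents do not show. Restricting to an interval would drop patients from the supportive analysis only. No extra patients or scans are needed.

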International guidelines offer opposing recommendations regarding VTE-prevention during leg-immobilization. The American College of Chest Physicians recommends no pharmacologic thromboprophylaxis, low molecular weight heparin (LMWH), due to the increased risk of bleeding in relation to the expected low effect of LMWH⁴. Furthermore, NICE, UK, recommends to consider offering LMHW to leg-immobilized patients after evaluating the risks of VTE and bleeding¹. Thus, today the clinical practice of VTE prevention in leg-immobilization varies considerably^{6 7}, and lacks strong evidence⁵.

The risk of VTE in association with trauma/surgery and leg-immobilization is high, with an estimated deep venous thrombosis (DVT) rate of 25% up to 50% after e.g. Achilles tendon rupture (ATR)^{8 9}. Today it is known that also asymptomatic DVTs often may result in pulmonary embolism¹⁰. Pharmacologic thromboprophylaxis (LMWH) in patients with lower-

leg immobilization has, however, shown to be low- or even non-effective in some studies^{5 7 3 4 11}. The latest meta-analysis of LMWH in leg-immobilized patients show only a moderate prevention on DVT because risk of bias and no preventive effect on pulmonary embolism⁵. Moreover, LMWH exerts adverse effects on the healing process¹² and increases the risk of bleeding complications^{3 4}. Thus, NHS, UK and SBU, Sweden have identified the need to develop safer and more efficient VTE-prophylaxis^{1 2 13}.

Mechanical thromboprophylaxis (IPC) reduces VTE, is a cost-effective intervention in hospitalized patients, and is recommended by guidelines for surgical patients^{1 14}. Whether IPC treatment applied during leg immobilization and performed in an outpatient setting can reduce the incidence of DVT is unknown. Therefore, mechanical thromboprophylaxis is not yet mentioned in guidelines for leg-immobilized patients. Recently, however, we published the first evidence that leg immobilized patients with ATR treated with adjuvant IPC exhibited a DVT-rate of 21% compared to 37% in the controls at 2 weeks. IPC intervention ended at two weeks, and thus at 6 weeks the DVT-rate was 50% in both groups⁹.

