The secondary outcome measure is patient-reported outcome (PRO) assessed with reliable and validated rating-scales (0-100 points); EuroQol (EQ-5D-5L), the Achilles Tendon total Rupture Score (ATRS), foot and ankle outcome score (FAOS), and Olerud-Molander Ankle Score (OMAS) at 6 and 12 months. Data of both groups (IPC vs. no IPC) will be presented by mean, median, standard deviation, and range. EQ-5D-5L is a validated, generic health-related quality of life measure consisting of five items each with a five-level answer possibility. Each combination of answers is converted into a health index score¹⁷. The EQ5D-index is measured on an interval scale and, thus, analyzed with parametrical statistics. ATRS (ordinal scale) is a validated ATR PRO measure¹⁸, while OMAS (ordinal scale) and FAOS (ratio scale) are validated for ankle fractures¹⁹. Functional evaluation of the ATR-healing will be performed by the validated heel-rise test at one year post-injury^{18 16}. Heel-rise height and work (continuous data) of both groups will be presented²⁰.

Callus production (continuous data) in ATR and ankle fracture (AF) patients will be assessed at six weeks using microdialysis followed by quantification of procollagens, which recently emerged as a method to assess tendon healing^{15 22 23}. For fracture healing quantification of bone formation markers (alkaline phosphatase, osteocalcin, and pro-collagen type I propeptide) will be performed.

VTE-preventive mechanisms will be analyzed at the six week visit by assessments of profibrinolysis and coagulation as well as by blood-flow quantification using ultrasound²⁴. Overall hemostatic potential (OHP), D-dimer, plasminogen activator inhibitor-1 (PAI-1), endogen trombin potential, trombin antitrombin complex, plasmin antiplasmin complex, tissue plasminogen activator/PAI complex will be assessed at Karolinska Institutet, Coag. Unit, Ass. Prof. [name]. Peak femoral blood velocity will be calculated using custom ultrasound software and compared with baseline values, while microcirculation and tissue oxygenation will be assessed by near-infrared spectroscopy (INVOS®)^{25 24}. These explanatory continuous data will be compared between the groups.

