Outcome: The primary outcome, VTE at 6 weeks post-immobilization, will best be assessed by screening CDU of DVTs. CDU is rapidly becoming the investigation of choice to confirm the diagnosis of DVT since it is non invasive. It is acceptable to patients, can easily be repeated several times and uses equipment, which is widely available. Thus consent, accrual and adherence in a trial are likely to be more easily achieved than with alternatives.

The primary outcome will be validated by the explanatory outcome of VTE-prevention, assessed by quantification of blood flow, profibrinolysis and coagulation factors from blood serum taken by a study nurse at the 6 weeks visit.

A long-term effect of IPC on VTE and healing will be confirmed by the secondary patient-reported outcome measures (PROM). We have data suggesting that an asymptomatic DVT affects PROM at 1 year¹⁶. The PROM will be assessed by the patient filling in the validated questionnaires (EQ-5D-5L, ATRS, FAOS, OMAS) at the 1 year visit at the physiotherapist, who will also perform the functional evaluations, i.e. heel-rise tests. If any patient will miss the 1 year visit, the questionnaires will be sent home to the patient.

An IPC effect on tissue healing will be corroborated by assessment of callus production. Callus production in ATR and AF patients is assessed at 6 weeks by microdialysis followed by quantification of procollagens¹⁵.

To further control that the outcome measures are registered correctly, independent data monitoring and help with data management will be performed by eg. Karolinska Trial Alliance (KTA). Major outcome events (including serious adverse events believed to be due to treatment) will be supplied. All data will be reported using an online system registration at Karolinska Institutet called RedCap, which is a validated patient reporting tool used at over 300 universities.

Trial Organization: The Steering Committee will consist of [name] (PI), [name] (VTE expert), [name] (VTE expert), [name] (Radiologist, compression Doppler ultrasound), [name] (Statistician), [name] (coordinating study nurse), [name] (bone healing), [name] (expert on patient-reported outcome), and [name] (Patient representative).

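### A single six-week blood sample can show whether markers differ by arm, but not that IPC prevents VTE through profibrinolysis, and it cannot validate the primary outcome

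*Combined protocol and SAP*

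**What the plan says.** Under *Research question*, one secondary question is causal: "Does IPC reduce VTE incidence by upregulation of profibrinolysis". *Variables and measures* sets the time of measurement: "VTE-preventive mechanisms will be analyzed at the six week visit by assessments of profibrinolysis and coagulation". It lists the assays (among them D-dimer, PAI-1, overall hemostatic potential and the thrombin and plasmin complexes) and plans a between-group comparison of these explanatory data.

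The Outcome paragraph of *Study Design (PICO)* repeats the timing, "profibrinolysis and coagulation factors from blood serum taken by a study nurse at the 6 weeks visit", and gives the markers their role: "The primary outcome will be validated by the explanatory outcome of VTE-prevention".

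The patient is sent for the primary compression duplex ultrasound (CDU) from the same visit, given as six weeks in the Intervention paragraph and six to eight weeks in the Comparator paragraph. No baseline or two-week blood sample is described. The only baseline named for a mechanism measure concerns flow: "Peak femoral blood velocity will be calculated using custom ultrasound software and compared with baseline values".

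The *Statistical analysis plan* provides t-tests or nonparametric tests for continuous secondary data. It contains no mediation analysis and no model relating markers to VTE. *Estimated sample size and power* allots 100 patients to the blood and microdialysis work.

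**The concern.** To say that IPC prevents VTE by way of profibrinolysis, one must at least show that the marker changed before the clot formed. A marker first measured when the outcome is read cannot show that order. The protocol's own background suggests that many clots form early. In the earlier Achilles trial the IPC patients "exhibited a DVT-rate of 21% compared to 37% in the controls at 2 weeks", and the paragraph on delay in the *Statistical analysis plan* accepts that a VTE may precede treatment. Some of the listed assays reflect clotting and lysis, so a clot, or drug treatment of one found before the visit, could itself move them.

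The word *validated* raises a separate problem of logic. A marker difference does not make a scan diagnosis more accurate, and the lack of one does not make it less so. The protocol supports the endpoint in another way, through masked review of positive and technically difficult scans.

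At stake is what the trial may conclude. Followed literally, the plan invites a report that the VTE result has been validated and its mechanism answered, from data that can establish neither.

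**Working it through.** **1. The plan's own figure.** The documents state that 100 patients give 90% power for the markers, but give no marker, difference or SD, so this cannot be reproduced. The difference it implies can be derived, taking alpha 0.05 as two-sided (sidedness is not stated): detectable difference = (1.960 + 1.282) × √(2/n per arm).
- If 100 is the total (50 per arm): 3.242 × √(2/50) = 0.65 SD.
- If 100 is per arm: 3.242 × √(2/100) = 0.46 SD.

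The documents do not say which is meant.

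**2. How many clots might precede the sample.** Inputs from *Survey of the Field*: two-week DVT 37% (control) and 21% (IPC); six-week DVT 50% in both arms.
- Control: 37/50 = 74%.
- IPC: 21/50 = 42%.

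Both shares assume that the two-week DVTs are counted in the six-week rate. The patients all had Achilles rupture, and IPC stopped at two weeks.

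**3. Can clots alone create an arm difference in a marker?** Take a marker with no preventive role that is shifted by d SD in patients with VTE (d is an assumption; the documents give none). Arm difference = (0.28 − 0.20) × d, using the planned rates.
- d = 0.25: 0.02 SD.
- d = 0.5: 0.04 SD.
- d = 1.0: 0.08 SD.

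In simulated trials of 50 per arm, this arm difference was significant in 4.9%, 5.0% and 6.7% of trials, close to the nominal 5%. To reach the detectable 0.65 SD, the clot effect would have to be 0.65/0.08, about 8 SD. With the rates the protocol held before its precautionary reductions (33% and a 40% relative reduction), the gap is 0.33 × 0.40 = 0.132, or 0.13 SD for d = 1.0, which is still small.

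The significance rates apply to the planned subset. With 1,260 patients sampled, the same 0.08 SD was significant in 28% of simulated trials.

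**4. Could a marker–VTE association show the route?** In the same simulated trials of 100, a logistic model of VTE on arm and marker found a significant marker effect in 18%, 53% and 98% of trials for d = 0.25, 0.5 and 1.0. The marker prevented nothing in any of them. An association at six weeks therefore cannot tell cause from consequence. The plan does not include this analysis; the check shows that adding it to the existing sample would not answer the causal question.

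**5. Can the subset corroborate the VTE result?** With 50 per arm, expected VTEs are 50 × 0.28 = 14 and 50 × 0.20 = 10, and power for the VTE difference is 15%. With 100 per arm it is 26%.

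**The case against.** The strongest defence is that the planned analysis is a randomised comparison of marker levels. Reverse causation hardly touches it (step 3), and it tests a necessary link in the proposed mechanism. The protocol calls these measures explanatory, and nothing in the primary analysis depends on them. All of this stands. It supports the narrower question of whether IPC changes the markers. It does not support the causal question or the word *validated*.

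A reader might infer more than the documents support:

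- *That a six-week arm difference would probably just reflect fewer clots.* On the planned rates the shift is about 0.08 SD for a 1 SD clot effect. Early anticoagulation cannot be sized from the documents. With no two-week scan planned, mainly symptomatic VTEs would be found and treated before the sample.
- *That three quarters of the clots here will precede the sample.* The 74% is one arm of an Achilles-only trial, and the other arm gives 42%. At least 1,000 of the 1,400 patients here have ankle fractures, for whom no two-week rate is given.
- *That the subset is too small for mediation analysis.* None is planned.
- *That serum is the wrong specimen.* The documents state no assay requirements, so the point would rest on outside laboratory knowledge.
- *That sampling after device removal hides the effect.* The protocol says "At the 2 and 6 weeks visit the orthosis will be removed by a nurse", but does not say whether blood and flow are taken before or after. This is missing detail, as is the time of the baseline velocity measurement.

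**Conclusion.** The concern holds in a limited form. The secondary question is causal and the Outcome paragraph claims validation, but one blood sample at the outcome visit, compared between arms, can deliver neither. It can validly show whether marker levels differ by allocation at six weeks.

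The conclusion rests on the timing and the planned analysis, not on any exact share of early clots. The 74% and 42% illustrate the timing problem under the assumptions in step 2. The 0.08 SD rests on the planned 28% and 20% and an assumed 1 SD clot effect.

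A null marker result would not refute the VTE result either. With 100 patients in total, 90% power is reached only for differences of about 0.65 SD, and the protocol itself lists blood flow as another possible mechanism. The primary endpoint, its masked review, the main sample size and the primary analysis are untouched. This is a correction to what the trial may claim.

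**What to change.** - In the Outcome paragraph of *Study Design (PICO)*, replace the statement that the explanatory measures validate the primary outcome with wording that they *will be described alongside* it.
- Under *Research question*, restate the mechanistic question as: *Does IPC change profibrinolysis, coagulation and blood-flow markers at six weeks compared with routine care?* Add that a difference will not be taken to explain the VTE result.
- Optionally, also report the marker comparison with patients who have VTE or take anticoagulants shown separately, labelled descriptive.

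These are wording changes with no added visit or test. The cost is that the sponsor gives up the mechanistic claim. Keeping that claim would need earlier blood samples and a prespecified mediation analysis, a larger undertaking.

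Two changes should not be made. Flow should not be measured by ultrasound with the device in place before the CDU, because an operator who also performs the scan would learn the allocation and the masking of the primary assessment would be at risk. The baseline velocity comparison should not be deleted; the sponsor should state when baseline is measured. The specimen type is likewise a detail for the sponsor to clarify.
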